5.7.5. ECGs

The information of ECG is captured in adverse events interpreted by investigators.

5.7.6. Assessment of Driving Incidents

Assessment of accidents/violations will be listed by patient (all randomized population). Summary table will be created (baseline and postbaseline)

5.7.7. Safety Topics of Interest

5.7.7.1. Cardiovascular Safety

Identification of Baseline Cardiovascular Disease: Identification of the subgroup of patients with baseline CVD was performed using medical history, reported by the patient at study entry. A patient was identified as having baseline CVD (“yes”) if the patient had 1 or more conditions that were part of the patients’ medical history or preexisting conditions in the following SMQs: Narrow terms in Cardiac arrhythmias (includes sub-SMQs; SMQ 20000049)

- Narrow terms in Cardiac failure (SMQ 20000004)
- Narrow terms in Cardiomyopathy (SMQ 20000150)
- Narrow terms in Central nervous system vascular disorders (includes sub-SMQs) (SMQ 20000060)
- Narrow terms in Embolic and thrombotic events (includes sub-SMQs) (SMQ 20000081)
- Narrow terms in Hypertension (SMQ 20000147)
- Narrow terms in Ischaemic heart disease (includes sub-SMQs) (SMQ 20000043)
- Pulmonary hypertension (SMQ 20000130)
- Torsade de pointes/QT prolongation (SMQ 20000001)

Identification of Patients with Cardiovascular Risk Factors:

CVRF is defined in Section 5.8.

Patients are summarized by the incremental presence of the above risk factors in two ways;

[1] 0 or 1 versus ≥ 2 (2 groups summary)

[2] 0, 1, 2, 3, 4, ...

Working Definitions

Definitions that were used to identify all CV AEs :

- *Potential CV AEs:* all PTs (for TEAEs and AEs) in the SMQs listed below plus PTs of abdominal pain, abdominal pain upper, and abdominal pain lower.

- *Likely CV AEs*: a subset of the potential CV AEs based on medical review and medical judgment

Potential Cardiovascular Adverse Events for the entire migraine population enrolled in the study were identified using the SMQs listed below (specifically broad and narrow terms) and then a listing of patients having an AE potentially CV in nature was generated. SMQ “narrow” terms included PTs that are highly likely to represent the condition of interest, while “broad” terms included additional PTs that may represent the condition of interest but may also prove to be of little or no interest upon closer inspection.

Broad and narrow terms in the following SMQs were used to analyze CV AEs:

- Cardiac arrhythmias (includes sub-SMQs; SMQ 20000049)
- Cardiac failure (SMQ 20000004)
- Cardiomyopathy (SMQ 20000150)
- Central nervous system vascular disorders (includes sub-SMQs; SMQ 20000060)
- Embolic and thrombotic events (includes sub-SMQs; SMQ 20000081)
- Hypertension (SMQ 20000147)
- Ischaemic heart disease (includes sub-SMQs; SMQ 20000043)
- Pulmonary hypertension (SMQ 20000130)
- Torsade de pointes/QT prolongation (SMQ 20000001)

The list of events and individual patient data were then medically reviewed to determine if the terms identified represented likely CV AE. For example, if an AE term “edema” was identified using the “Cardiac failure” SMQ broad list in a patient who experienced this AE after taking the study drug, and at the same time also reported dyspnea, had a medical history of hypertension, was taking concomitant ace-inhibitor + hydrochlorothiazide, or recently started a separate diuretic, then based on this information the AE of “edema” would represent a likely CV AE.

The listing of all potential CV AEs with reason(s) for whether or not the events were considered likely CV is provided for all randomized population. Events that are “treatment emergent” are flagged.

Following summary will be created:

- Summary and Analysis of Potential CVAE within SMQ
- Summary and Analysis of Likely CVAE within SMQ, PT
- Summary and Analysis of Likely CVTEAE within SMQ, PT
- Summary and Analysis of Potential CVAE by CVRFs by SMQ
- Summary and Analysis of Likely CVAE by CVRFs by PT
- Summary and Analysis of Likely CVTEAE by CVRFs by PT

- Patient Listing for Likely CV AEs in Patients with Categorical Changes of Interest in Vital Signs (Pulse, SBP, DBP)
- Summary and Analysis of Likely Cardiovascular Adverse Events in Patients with Categorical Changes of Interest in Blood Pressures and Pulse.

Note: In this analysis, patients with a categorical change of interest in BP or pulse (defined in [Table LAIH. 5.4](#)) are used as the denominator whereas the numerator represents the number of patients reporting a likely CV AE. The summary is based on

- SMQ
- Patients with at least one Narrow scope PT in the SMQ
- Patients with at least one Narrow or Broad scope PT in the SMQ

Concomitant Cardiovascular Medications

Cardiovascular medications were identified using the World Health Organization's ATC/Defined Daily Dose codes from a listing of all concomitant medications. These were summarized based on ATC2 codes within the "Cardiac System," as well as medications within the ATC2 code of "Antithrombotic agents" in the categories as described in [Table LAIH. 5.5](#).

Table LAIH. 5.5 Identified Cardiovascular Medications Anatomical Therapeutic Chemical (ATC)/Defined Daily Dose

C01, Cardiac Therapy	C07, Beta-Blocking Agents
C02, Antihypertensives	C08, Calcium Channel Blockers
C03, Diuretics	C09, Agents Acting On The Renin–Angiotensin System
C04, Peripheral Vasodilators	C10, Lipid-Modifying Agents
C05, Vasoprotectives	B01, Antithrombotics

The selected medications were then reviewed by Lilly Medical to confirm that the indication for use was a CV condition (per medical history or AE). For example, any medications whose indication for use was "primary study condition" were removed because many of the CV medications are also used for migraine treatment (for example, beta blockers and calcium channel blockers).

5.7.7.2. Hepatic Safety

The percentages of patients with potentially drug-related hepatic disorders were summarized by treatment using the MedDRA PTs contained in any of the following SMQs, separately for AEs and TEAEs. Cases were then subsequently medically reviewed:

- Broad and narrow terms in the Liver-related investigations, signs, and symptoms (SMQ 20000008)
- Broad and narrow terms in the Cholestasis and jaundice of hepatic origin (SMQ 20000009)
- Broad and narrow terms in the Hepatitis, noninfectious (SMQ 20000010)

- Broad and narrow terms in the Hepatic failure, fibrosis, and cirrhosis and other liver damage (SMQ 20000013)
- Narrow terms in the Liver-related coagulation and bleeding disturbances (SMQ 20000015)

Hepatic events (AEs which can be beyond 48 hours) in the above SMQs will be summarized for safety population.

Treatment-emergent hepatic events in the above SMQs will be summarized for safety population.

Hepatic events (AEs which can be beyond 48 hours) listing with TEAE flag will be created for safety population.

5.7.7.3. Injuries and Accidents Secondary to Neurologic Adverse Events

In order to accurately capture reported injuries and accidents, all AEs in the Injury, Poisoning, and Procedural Complications SOC were reviewed. These AEs were not limited to a treatment-emergent time period (that is, 48 hours postdose). Each AE of injury, poisoning, and procedural complication was medically reviewed in order to determine if a neurologic TEAE (from the Nervous system disorders SOC) either preceded or occurred concurrently with the AE.

Following TFL will be created.

- Listing of Neurologic TEAE (already medical reviewed),
where “Neurologic TEAE timing <= injury timing”
- Listing of Neurologic TEAE (NOT medical reviewed),
where “Neurologic TEAE timing <= injury timing”
- Summary of “Neurologic TEAEs” and “AEs SOC=Injury, Poisoning, and Procedural Complications”
- Summary of all PTs related to the Injury, Poisoning, and Procedural Complications SOC

5.7.7.4. Suicidal Ideation and Behavior and Nonsuicidal Self-Injurious Behavior

A summary table of PTs within the Suicide/Self Injury SMQ (20000037) is provided for safety population. All AEs are presented (after Visit 1 through Visit 3.)

5.7.7.5. Hypersensitivity Events

Potential hypersensitivity reactions (**including anaphylaxis**) were summarized using the MedDRA PTs contained in any of the following SMQs for TEAEs (considered potential immediate hypersensitivity reactions) and AEs (considered potential non-immediate hypersensitivity reactions).

- Anaphylactic reaction SMQ (20000021; narrow, algorithm per SMQ guide, and broad)
- Hypersensitivity SMQ (20000214; narrow and broad)
- Angioedema SMQ (20000024; narrow and broad)

Following TFL will be created:

- Listing: Potential Immediate Hypersensitivity (<=48hours)
- Listing: Potential Non-Immediate Hypersensitivity (> 48hours)
- Summary: Potential Immediate Hypersensitivity (<=48hours)
- Summary: Potential Non-Immediate Hypersensitivity (> 48hours)

Note 1: Two listing above do not overlap. Two tables above do not overlap.

Note 2: All TFLs above are before medical review.

5.7.7.6. Serotonin Syndrome

Potential cases of Serotonin Syndrome (TEAE) are identified based on the following conditions;

- SMQ of Neuroleptic Malignant Syndrome (SMQ 20000044)
- PT terms of orthostatic hypotension, urinary incontinence, urinary retention, oesophageal dysmotility, gastroparesis, diarrhoea, faecal incontinence, constipation, muscle twitching, muscle stiffness, and muscle spasm.

The summary of the above TEAE will be created.

Then medical review is conducted for these TEAEs. These TEAEs are reviewed, and cases which preliminarily appeared that they might meet the Hunter or Sternbach criteria were then thoroughly evaluated for information including associated AEs, timing of AEs, severity, seriousness, concomitant medications, and medical history.

The listing will be created.

Note: The 2 validated sets of diagnostic criteria are the Hunter Serotonin Toxicity Criteria (Dunkley et al. 2003) and Sternbach Criteria (Sternbach 1991), with the former being more sensitive and specific.

5.7.7.7. Dizziness, Vertigo, and common TEAE

For patients experienced TEAE with PT including “Vertigo” term (Vertigo, Cervicogenic vertigo, Vertigo CNS origin, Vertigo positional, and Vertigo labyrinthine), summary of Vertigo findings will be created. The TFLs include [S1]-[S6] as specified below.

Note 1: If TEAE starting “hour” is missing, then starting hour is set as on the day of 0:00.

Note 2: If TEAE ending “hour” is missing, then ending hour is set as on the day of 23:59.

Note 3: If TEAE ending “day” and “hour” are missing, then ending day is set as Visit 3 day and hour is set as on the day of 23:59.

[S1] Frequency and Proportion of the TEAE

Note: The denominator= the number of the safety population.

[S2] Frequency of the severity (mild/moderate /severe)

[S3] The TEAE Onset time from dosing (Q1, Q2=median, Q3) (units=hours)

For this analysis, use two different methods to derive onset time from dosing:

[1] All TEAEs, including events with TEAE start time imputation.

[2] TEAEs which have non-missing TEAE start time.

[S4] Duration of the TEAE (Q1, Q2=median, Q3) (units=hours)

For this analysis, use two different methods to derive duration:

[1] All TEAEs, including events with TEAE start time imputation or end time imputation.

[2] TEAEs which have non-missing TEAE time (both start time and end time.)

[S5] Frequency and Proportion of “No interference with daily activity at 2 hours”

Note: The denominator= the number of patients who experienced the TEAE within the safety population.

[S6] Frequency and Proportion of “PGIC = better/much better at 2 hours”

Note : The denominator= the number of patients who experienced the TEAE within the safety population.

The same summary table [S1]-[S6] will be created for those who experienced TEAE with PT=Dizziness.

For common TEAE (an incidence in any lasmiditan group $\geq 1.5\%$), [S1], [S2], [S3], and [S4] will be created.

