5.1. Overall Design

Study LAIH is a prospective, multicenter, randomized, double-blind, placebo-controlled Phase 2 study of Japanese adult patients suffering from migraine with or without aura. Patients will have a history of migraine for at least 1 year, 3 to 8 migraine attacks per month, and disabling migraine as defined by a Migraine Disability Assessment Test (MIDAS) score ≥ 11 . Patients will be asked to treat a single migraine attack with study drug on an outpatient basis. At Visit 2, patients will be provided with doses for treatment of an attack; placebo, lasmiditan 50 mg, 100 mg, or 200 mg will be assigned.

[Table LAIH.1](#) shows the treatment group assignments for this study.

Each patient's study participation will consist of a screening visit (Visit 1), followed by a randomization visit (Visit 2) 7 to 30 days after screening, a treatment period of up to 8 weeks, and an EoS visit (Visit 3) 3 to 28 days after treating the migraine attack (or at 8 weeks [+2 weeks as visit allowance] after Visit 2). If a migraine attack is treated, the EoS visit must occur no later than 28 days following treatment of the migraine attack. Sites will encourage patients to visit as early as possible following treatment of the migraine attack.

[Figure LAIH.1](#) illustrates the study design.

Abbreviations: EDC = early discontinuation; EoS = end of study.

- a Preventive treatment allowed (if stable 3 months prior to Visit 1).
- b Patients will take 3 tablets to maintain blinding.
- c Patients will wait to take study drug until migraine pain is moderate/severe; must be the FIRST treatment for the migraine taken within 4 hours of pain onset.
- d Patients who do not treat a migraine with study drug should attend Visit 3 at 8 weeks after Visit 2. Visit 3 should be finished by 8 weeks (+14 days as visit allowance) after Visit 2.

Figure LAIH.1. Patient flow overview Clinical Protocol H8H-JE-LAIH.

Study governance considerations are described in detail in [Appendix 3](#).

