5.4. Justification for Dose

Three doses (lasmiditan 50 mg, 100 mg, and 200 mg) used in the Study 302/LAHK (study for bridging reference), have been selected in this Study LAIH in Japanese patients with migraine. Two single-attack Phase 3 studies (Study 301/LAHJ and Study 302/LAHK) of lasmiditan have been completed, and these studies show dose-dependent efficacy of lasmiditan versus placebo to increase freedom from headache pain with lasmiditan. All doses (50 mg, 100 mg, and 200 mg) showed statistically significant superiority versus placebo on pain freedom, MBS freedom, and pain relief. In general, the efficacy of lasmiditan was dose dependent, with lasmiditan 50 mg showing the least efficacy and lasmiditan 200 mg showing the most efficacy. Safety analysis showed TEAEs were increased with lasmiditan compared to placebo, with the most common AEs being dizziness, paresthesia, somnolence, fatigue, and nausea. In general, these TEAEs were observed to increase in a dose-dependent manner (i.e., they were lowest with lasmiditan 50 mg and highest with lasmiditan 200 mg). These TEAEs were usually mild to moderate in severity with a median duration of 1 to 5 hours.

6. Study Population

Prospective approval of protocol deviations to recruitment and enrollment criteria, also known as protocol waivers or exemptions, are not permitted.

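### TEAE duration with no recorded end day is either run to Visit 3 as if observed or dropped, with no separation of ongoing events from events that ended on an unknown day (SAP 5.7.7.7, Note 3 and [S4])

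*SAP*

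**What the plan says.** SAP 5.7.7.7 specifies the summary labelled "Duration of the TEAE (Q1, Q2=median, Q3) (units=hours". It applies to TEAEs with a vertigo term and to common TEAEs (incidence of at least 1.5% in any lasmiditan group). For dizziness the section adds: "The same summary table [S1]-[S6] will be created for those who experienced TEAE with PT=Dizziness".

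Duration is derived in two ways:
- Method [1]: "All TEAEs, including events with TEAE start time imputation or end time imputation". Under Note 3, if the end day and hour are missing, "then ending day is set as Visit 3 day and hour is set as on the day of 23:59".
- Method [2]: "TEAEs which have non-missing TEAE time (both start time and end time").

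No third rule is given, and the section does not distinguish an event ongoing at Visit 3 from one that ended on a day nobody recorded. Censoring is specified in SAP 5.4.1, but only for the efficacy time-to-event endpoints.

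Protocol 5.1 places "an EoS visit (Visit 3) 3 to 28 days after treating the migraine attack". On TEAE duration in the earlier Phase 3 studies, Protocol 5.4 says: "These TEAEs were usually mild to moderate in severity with a median duration of 1 to 5 hours".

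**The concern.** An event expected to last a few hours can be given a duration of days or weeks that is set by when the patient came for Visit 3. The alternative row removes the event altogether, which is harmless only if a missing end is unrelated to how long the event lasted.

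Short, self-limiting events are part of the benefit/risk argument in Protocol 3.3, and [S4] is where duration in Japanese patients will be described. If the two rows differ, a reader cannot tell which is closer to the truth, because the table does not say how many events lacked an end or why.

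The point is about a missing end day. The start-hour rule (Note 1) and the end-hour rule (Note 2) are not at issue.

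**Working it through.** The plan states no figure that rests on the duration rule, so there is nothing to reproduce. The check is of consequences.

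**Inputs from the documents**
- Visit 3 is 3 to 28 days after dosing (Protocol 5.1). To 23:59 of the visit day this is about 3 × 24 = 72 h to 28 × 24 + 24 = 696 h from dosing.
- TEAE onset is within 48 h of dosing (SAP 5.7.1), so the imputed duration can be as short as 72 − 48 = 24 h. For onset soon after dosing it is about 72 to 696 h.
- Typical median duration is 1 to 5 h (Protocol 5.4).
- Planned arm sizes for the three lasmiditan doses are 81, 190 and 163 (SAP 5.2), used here as a stand-in for the safety population.
- Dizziness incidence at 100 and 200 mg was 15.4% to 17.2% (Protocol 3.2).

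**Assumptions not in the documents**
- Durations are lognormal with median 3 h and log-SD 1, so quantile(p) = 3 × exp(z_p) and the true quartiles are 1.5 / 3.0 / 5.9 h.
- Onset is soon after dosing, and imputed durations are uniform over 72 to 696 h.
- The share f of events with no end day is 5% to 30%.

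**Case A: the event ended, end day unknown at random.** Imputed values lie above essentially all real ones. While p < 1 − f, the method [1] quantile at p is therefore the true quantile at p/(1 − f). Example: f = 20%, p = 0.75 gives 0.75/0.80 = 0.9375, z = 1.534, and 3 × exp(1.534) = 13.9 h. At f = 30%, the upper quartile lies (0.75 − 0.70)/0.30 = 1/6 of the way into the imputed values: 72 + 624/6 = 176 h.

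| f | Method [1] lower / median / upper (h) | Method [2] (h) |
|---|---|---|
| 5% | 1.6 / 3.2 / 6.7 | 1.5 / 3.0 / 5.9 |
| 10% | 1.7 / 3.5 / 7.9 | 1.5 / 3.0 / 5.9 |
| 20% | 1.8 / 4.1 / 13.9 | 1.5 / 3.0 / 5.9 |
| 30% | 2.1 / 5.3 / 176 | 1.5 / 3.0 / 5.9 |

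Here method [1] is too long and method [2] is right. Simulation of 200,000 events agrees to within simulation error.

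**Case B: the event is ongoing at Visit 3.** The true duration exceeds the imputed one. At f = 20% method [1] is correct (1.8 / 4.1 / 13.9 h) and method [2] is too short (1.5 / 3.0 / 5.9 h). At f = 30%, if true durations are 1.5 times the time to Visit 3, the true upper quartile is 1.5 × 176 = 264 h, so method [1] understates it.

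**Case C: longer events are the ones without an end day.** If the longest share f is lost, the method [2] quantile at p is the true quantile at p(1 − f). At f = 20% the median sits at 0.40 (2.3 h) and the upper quartile at 0.60 (3.9 h). If the chance of a missing end merely rises in proportion to the rank of duration, averaging 20%, method [2] gives a median of 2.6 h and an upper quartile of 5.0 h; method [1] gives 3.5 h and 12.1 h.

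**When the upper quartile reaches the imputed values.** Assume the upper quartile is the first ordered value at or beyond 0.75n, averaged with the next when 0.75n is a whole number.
- Dizziness: 163 × 0.154 = 25.1 to 190 × 0.172 = 32.7 events per arm. With 25 events it is the 19th value, so 7 missing end days suffice; with 33 it is the 25th, so 9 suffice.
- Rare common TEAEs: the 1.5% threshold is 81 × 0.015 = 1.2, 163 × 0.015 = 2.4 and 190 × 0.015 = 2.9, so an event qualifies with 2 or 3 patients in one arm. With 2 or 3 events the upper quartile is the largest value; with 4 it is the mean of the two largest. One missing end day makes it depend on the Visit 3 date.

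**What a censored summary adds.** Take 10% ongoing and 10% date-unknown at random, with only onset known for the latter, so that they add no duration information. The ongoing share among informative events is 0.10/0.90 = 11.1%, and the Kaplan-Meier upper quartile is the true-duration quantile at 0.75/0.889 = 0.844.

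| | Lower / median / upper (h) |
|---|---|
| Truth | 1.7 / 3.4 / 7.9 |
| Kaplan-Meier | 1.7 / 3.5 / 8.2 |
| Method [1] | 1.8 / 4.1 / 13.9 |
| Method [2] | 1.5 / 3.0 / 5.9 |

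**The case against.** The case against has force on five points.

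- Quartiles depend on a long value only through its rank. Kaplan-Meier with every unended event censored at Visit 3 gives the same quartiles as method [1] until a quartile falls among the imputed values. At 20% missing the two agree exactly. This stands, so the gain comes from separating the two kinds of missing end, and from reporting a quartile as not reached where it falls among censored times.
- A reader might infer that method [1] always inflates duration. The documents do not support that: for an event ongoing at Visit 3 the imputed time is a lower bound.
- A reader might also infer that the upper quartile under method [1] generally reflects visit scheduling. It does so only from about 25% missing in a cell. At 10% and 20% missing it is 7.9 and 13.9 h, well below 72 h. No document gives the missing share. Patients are reminded daily to record adverse events (Protocol Section 2), and termination time is a recorded field (Protocol 9.2), so few end days may be missing.
- Protocol 9.2 lists onset and termination times and mentions no time at which an event was last known to be present. If only onset is available, censoring a date-unknown event there is the same as dropping it. This stands: that part of the fix cannot repair Case C without further data.
- Both methods are already to be shown, and SAP 5.4 makes safety output descriptive with no tests, so [S4] does not test the short-duration argument. This also stands and limits the importance.

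Printing both rows still does not settle the matter. Neither is right when ongoing and date-unknown events are mixed, and without counts a reader cannot judge which error dominates.

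**Conclusion.** The point holds as a minor one. Method [1] is too long for events that ended on an unrecorded day and a lower bound for those still ongoing. Method [2] is too short when longer or ongoing events are the ones without an end. The plan neither separates nor counts the two kinds.

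Under the stated assumptions, the median under method [1] moves from 3.0 h to between 3.2 and 5.3 h over 5% to 30% missing at random. The upper quartile moves from 5.9 h to between 6.7 and 13.9 h up to 20%, then jumps to about 176 h at 30%. For dizziness the jump needs roughly 7 to 9 missing end days in an arm; for the rarest common TEAEs it needs one.

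The size rests on the assumed lognormal shape, the spread of Visit 3 dates and above all the missing share, none of which the documents give. Alpha, power, sample size and T1 to T3 are untouched.

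**What to change.** In SAP 5.7.7.7 [S4]:
1. Classify each TEAE without an end day as ongoing at Visit 3 or as resolved with the end day unknown, and show both counts per arm.
2. Report Kaplan-Meier quartiles of duration by arm. Censor ongoing events at Visit 3. Censor date-unknown events at the last recorded time the event was present; state that where only onset is recorded they add no duration information.
3. Give a quartile as not reached where that is the result.
4. Keep methods [1] and [2] as supplementary rows.

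The cost is SAP wording and one standard procedure for a descriptive safety table, plus a check that the eCRF allows the classification in step 1. The downside is that upper quartiles may not be estimable in small cells. That is an accurate statement of what such cells contain, and the supplementary rows remain available.
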